8.3.3 CLASSIFICATION OF AN ADVERSE EVENT

8.3.3.1 SEVERITY OF EVENT

For AEs, the following guidelines will be used to describe severity.

- **Mild** – Events require minimal or no treatment and do not interfere with the participant's daily activities.
- **Moderate** – Events result in a low level of inconvenience or concern with the therapeutic measures. Moderate events may cause some interference with functioning.
- **Severe** – Events interrupt a participant's usual daily activity and may require systemic drug therapy or other treatment. Severe events are usually potentially life-threatening or incapacitating. Of note, the term "severe" does not necessarily equate to "serious".

8.3.3.2 RELATIONSHIP TO STUDY INTERVENTION

All AEs must have their relationship to study intervention assessed by the investigator or qualified clinician who evaluates the participant based on temporal relationship and their clinical judgment. The degree of certainty about causality will be graded using the categories below.

- **Definitely Related** – There is clear evidence to suggest a causal relationship, and other possible contributing factors can be ruled out. The clinical event, including an abnormal laboratory test result, occurs in a plausible time relationship to study intervention administration and cannot be explained by concurrent disease or other drugs or

Title: *The BREATHE Study: Bronchiolitis Recovery and the Use of High Efficiency Particulate Air (HEPA) Filters*

Sponsor: ISCPTN DCOC

chemicals. The response to withdrawal of the study intervention (dechallenge) should be clinically plausible. The event must be pharmacologically or phenomenologically definitive, with use of a satisfactory rechallenge procedure if necessary.

- **Probably Related** – There is evidence to suggest a causal relationship, and the influence of other factors is unlikely. The clinical event, including an abnormal laboratory test result, occurs within a reasonable time after administration of the study intervention, is unlikely to be attributed to concurrent disease or other drugs or chemicals, and follows a clinically reasonable response on withdrawal (dechallenge). Rechallenge information is not required to fulfill this definition.
- **Potentially Related** – There is some evidence to suggest a causal relationship (e.g., the event occurred within a reasonable time after administration of the intervention). However, other factors may have contributed to the event (e.g., the participant's clinical condition, other concomitant events). Although an AE may rate only as "possibly related" soon after discovery, it can be flagged as requiring more information and later be upgraded to "probably related" or "definitely related", as appropriate.
- **Unlikely to be related** – A clinical event, including an abnormal laboratory test result, whose temporal relationship to study intervention administration makes a causal relationship improbable (e.g., the event did not occur within a reasonable time after administration of the study intervention) and in which other drugs or chemicals or underlying disease provides plausible explanations (e.g., the participant's clinical condition, other concomitant treatments).
- **Not Related** – The AE is completely independent of study intervention administration, and/or evidence exists that the event is definitely related to another etiology. There must be an alternative, definitive etiology documented by the clinician.

8.3.3.3 EXPECTEDNESS

The site investigator or qualified clinician designee will be responsible for determining whether a severe AE or SAE is expected or unexpected. A severe AE or SAE will be considered unexpected if the nature, severity, or frequency of the event is not consistent with risks of underlying chronic medical conditions, is not an event measured in study data collection (hospitalization, ED visit, etc.), or is not related to function of the study intervention equipment.

Potential expected events could include the following:

- Cough
- Wheeze
- Trouble breathing
- Medical or emergency department/urgent care visit for respiratory complaint

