2.3 RISK/BENEFIT ASSESSMENT

2.3.1 KNOWN POTENTIAL RISKS

This study poses minimal risk to participants. Possible risks include the following:

- There is potential for false reassurance that the intervention prevents all adverse home environmental exposures.
- Noise produced by the device may be considered by some to be a “white noise” but could be bothersome or harmful if the highest setting is used continuously in close proximity to the child.
- The device may take up space, causing inconvenience.
- Participating individuals could be injured or experience electrical shock during instrument installation or use in the home (childproofing required).

Methods of reducing risk are discussed in Section 2.3.3.

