- **Healthcare visits:** The parent/guardian will record the number of hospitalizations, ED/UC visits, and other medical visits for respiratory symptoms. This will be a (Y/N) for whether they participant (child) had a healthcare visit in the past week. If Y, there will be a prompt to enter the number of visits for each visit type. If N, they will move on to the next section, "Time away from home."
- **Time Away from home:**
 - **Days away from home:** The parent/guardian will be prompted to enter how many days that week the child spent more than 6 hours outside the home (0-7 days).
 - **Nights away from home:** The parent/guardian will be prompted to enter how many nights that week the child spent away from their primary residence (away for vacation, staying with someone else, etc.) (0-7 days).
- **Equipment use:**
 - **HEPA/control unit use:** For each room with a HEPA/control unit, the parent/guardian will be asked to respond Yes/No to whether they used unit and asked to report the usual setting used (1, 2, 3, or 4). If applicable, the parent(s)/guardian(s) will also record the numerical reading visible on the kW meter attached to each HEPA/control unit. This will be a simple entry of the numbers displayed on the kW meter to respond to the survey prompt.
 - **PurpleAir monitor:** The parent/guardian will be asked whether the monitor is plugged in with the light on (Yes or No). They will also be asked whether the hot spot is on with bar light and 3 lighted dots on (Yes or No).

Quality of Life:

- The PedsQL™ Pediatric Quality of Life Inventory Infant Scales⁹⁸ questionnaire will be administered to a parent/guardian at the end of the intervention period. This is a validated outcome measure of QOL for infants 1-12 months (36 items) and 13-24 months (45 items). The constructs include 5 subdomains: physical functioning, physical symptoms, emotional functioning, and cognitive functioning.

The questionnaire will be administered online. The alternative will be for the research coordinator to obtain responses verbally.

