8.4 UNANTICIPATED PROBLEMS

8.4.1 DEFINITION OF UNANTICIPATED PROBLEMS (UPIRTSOS)

Unanticipated problems (UPs or UPIRTSOS) involving risks to participants or others include, in general, any incident, experience, or outcome that meets all of the following criteria:

- Unexpected in terms of nature, severity, or frequency given (a) the research procedures that are described in the protocol-related documents, such as the Institutional Review Board (IRB)-approved research protocol and informed consent document; and (b) the characteristics of the participant population being studied;
- Related or possibly related to participation in the research (“possibly related” means there is a reasonable possibility that the incident, experience, or outcome may have been caused by the procedures involved in the research); and
- Suggests that the research places participants or others at a greater risk of harm (including physical, psychological, economic, or social harm) than was previously known or recognized.

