### **6.7.1 Adverse Events**

Adverse events constitute any untoward or unfavorable occurrence in a research participant associated with the involvement in the research that may or may not be related to their participation in research. The adverse events will be collected and coded in accordance with the guidelines specified in MedDRA/CTCAE.

Unexpected adverse events refer to adverse events occurring in participants when they deviate from the following guidelines:

- Risks outlined in study-related documents (e.g. approved research protocol, investigator brochure)
- Anticipated course of any pre-existing health conditions, diseases, or disorders in the affected individuals, considering their specific risk factors.

The analysis and listing of adverse events will be done for safety population. The summary statistics will be presented (if applicable) by organ class, study groups, study phase, severity, expectedness, and relatedness to the study intervention. The severity for adverse events will be presented as per the guidelines specified by “The Common Terminology Criteria for Adverse Events” (CTCAE) developed by the US National Cancer Institute (NCI).

Adverse events will be analyzed and listed as per the guidelines listed below:

1. If a participant experiences same AE multiple times during the study, the patient will be counted only once in the number of participants experiencing the event.

2. If a patient experiences same AE multiple times but with different severities during the study, the worst or most intense event will be counted.
3. If there are adverse events that are not coded, the summary table will use the exact description as reported in the database. The statistician may consult with the study investigator for further information to resolve this (i.e. whether it can be reassigned to one of the existing coding). Any decisions made in this regard will be documented (either by including as a footnote or as an appendix).

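### The expectedness rule in protocol Section 8.3.3.3 contradicts its own list when read with 'or', makes equipment relation a ground for 'expected' when read with 'and', and matches neither protocol 8.4.1 nor SAP 6.7.1

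*Protocol*

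**What the plan says.** Protocol Section 8.3.3.3 makes the site investigator or a qualified clinician responsible for "determining whether a severe AE or SAE is expected or unexpected". It gives three grounds for 'unexpected'. The first concerns the nature, severity or frequency of the event, and is met when "the event is not consistent with risks of underlying chronic medical conditions". The second and third are that the event "is not an event measured in study data collection (hospitalization, ED visit, etc.), or is not related to function of the study intervention equipment". The three are joined by 'or'.

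A list of potential expected events follows directly: cough, wheeze, trouble breathing, and "Medical or emergency department/urgent care visit for respiratory complaint". Hospitalization is not on the list, although the second ground names it as a measured event.

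Two other places define the same word.

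- Protocol Section 8.4.1 makes it the first element of an unanticipated problem: "Unexpected in terms of nature, severity, or frequency given (a) the research procedures that are described in the protocol-related documents", together with the characteristics of the study population.
- SAP Section 6.7.1 calls an AE unexpected when it deviates from "Risks outlined in study-related documents (e.g. approved research protocol, investigator brochure", or from the anticipated course of pre-existing conditions. The same section plans AE summaries by expectedness, if applicable.

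**The concern.** A clinician has to turn the sentence in 8.3.3.3 into a yes-or-no answer, and the two natural ways to read it give opposite answers for the commonest events in this population. Neither reading is satisfactory. One contradicts the examples printed below the sentence. The other makes a link to the study device a reason to call an event expected, although the link to the device is what the causality grading in Section 8.3.3.2 exists to assess.

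The classification feeds a planned summary. The SAP splits AEs by expectedness under its own definition, but the protocol has the site make the call under another. A table headed 'unexpected' could therefore contain events that the SAP's definition would not put there, and omit events that it would.

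**Working it through.** No numerical figure is at issue, so the check is a truth table followed by a comparison of the three definitions.

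**Step 1. The conditions.** From Section 8.3.3.3:

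- A = the event is consistent with the risks of a chronic condition
- B = the event is measured in study data collection
- C = the event is related to the function of the equipment

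The 'or' reading is: unexpected = not A, or not B, or not C. The 'and' reading is: unexpected = not A, and not B, and not C.

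| A | B | C | 'or' | 'and' |
|---|---|---|---|---|
| no | no | no | unexpected | unexpected |
| no | no | yes | unexpected | expected |
| no | yes | no | unexpected | expected |
| no | yes | yes | unexpected | expected |
| yes | no | no | unexpected | expected |
| yes | no | yes | unexpected | expected |
| yes | yes | no | unexpected | expected |
| yes | yes | yes | expected | expected |

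These are counts of logical combinations, not of patients or events.

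**Step 2. The 'or' reading.** Seven of 8 combinations are unexpected, and all 4 with C = no are among them. Take a severe wheeze or a respiratory ED visit that has nothing to do with the unit. C is 'no', so the event is unexpected whatever A and B are, yet it is on the list of expected events. A listed event is expected only in the last row, where it fits a chronic condition and is also related to equipment function.

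**Step 3. The 'and' reading.** One of 8 combinations is unexpected. Cough, wheeze, trouble breathing and respiratory visits are all collected in the weekly survey (protocol Section 8.1), so B = yes and they are expected, as the list intends. With C = yes, however, 0 of 4 combinations are unexpected. A severe event from a unit fault of a kind that Section 2.3.1 does not describe would be expected solely because the unit's function produced it. With B = yes, 0 of 4 are unexpected either, whatever the severity or frequency.

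**Step 4. Hospitalization.** Clause B names hospitalization with no qualifier. Section 8.1 says what the survey measures: "The parent/guardian will record the number of hospitalizations, ED/UC visits, and other medical visits for respiratory symptoms". If the parenthesis in 8.3.3.3 is taken alone, any admission has B = yes and is expected under 'and'. If it is read with Section 8.1, only respiratory admissions have B = yes. A non-respiratory admission unrelated to the equipment, in a child with no relevant chronic condition, then falls in the first row and is unexpected. The text does not settle which is meant, and the list does not help because it omits hospitalization.

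**Step 5. The three definitions side by side.**

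| | Protocol 8.3.3.3 | Protocol 8.4.1 | SAP 6.7.1 |
|---|---|---|---|
| Applies to | severe AEs and SAEs | candidate unanticipated problems | AEs |
| Risks described in study documents | not mentioned | yes | yes |
| Participant's condition or population | chronic conditions only | study population | course of pre-existing conditions |
| Measured-event clause | yes | no | no |
| Equipment clause | yes | no | no |

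Two of the three grounds in 8.3.3.3 appear in neither of the other definitions. The standard that the other two share, the described risks, is missing from 8.3.3.3.

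**Step 6. What depends on the rule.** Protocol Sections 8.3.1 and 8.3.4 require severe AEs, SAEs and AEs associated with the intervention or equipment to be recorded whatever their expectedness. Section 8.3.6 makes evidence of causality the trigger for immediate reporting of an SAE that is also a study endpoint. Section 8.4.1 carries its own test, and Section 8.4.2 asks for potential unanticipated problems as well. What remains exposed is the site's classification and the SAP's expectedness summaries.

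**The case against.** The best defence is that the examples show what the authors meant. A clinician would see that respiratory symptoms and visits are expected and would not apply the literal 'or', which makes nearly everything unexpected. The list is also hedged as potential. The SAP has its own definition for its own tables, shows expectedness only if applicable, and is descriptive here; no test, boundary or stopping rule uses it. The manual of procedures, the safety monitoring plan and the DSMB charter may give working guidance and are not available for this review.

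Much of this stands. It limits the consequence, and it means that divergence between the roughly 17 hospitals (protocol Section 10.1.4) is a possibility, not something the documents show. It does not repair the sentence. Following the examples leads to the 'and' reading, and that reading has the equipment problem. The SAP's separate definition does not help either, because the protocol still has the site classify under different words.

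Three stronger conclusions are tempting, and the documents do not support them.

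- *Related and unexpected events would go unflagged.* No recording or reporting route in protocol Sections 8.3.1, 8.3.4, 8.3.6, 8.4.1 or 8.4.2 passes through this rule.
- *Every hospitalization becomes expected, so the rule separates nothing.* Read with Section 8.1, the 'and' reading does separate respiratory from non-respiratory admissions.
- *Every injury caused by the equipment becomes expected.* The clause is about the function of the equipment, which is narrower. Some such harm is also already a described risk: "Participating individuals could be injured or experience electrical shock during instrument installation or use in the home (childproofing required". A shock could therefore be expected in nature under a sound definition too, unless its severity or frequency was out of line.

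**Conclusion.** The point holds as a defect of definition. Under 'or', the rule contradicts the list below it for any listed event unrelated to the equipment (4 of 4 such combinations unexpected). Under 'and', it leaves no room for an unexpected event related to equipment function (0 of 4) and so merges expectedness with the causality grading of Section 8.3.3.2. Under both readings it departs from protocol Section 8.4.1 and SAP Section 6.7.1, and the status of hospitalization is unresolved.

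The harm is limited to misclassified severe AEs and SAEs and expectedness tables that do not match the SAP's definition. No event is lost, and efficacy inference is untouched. The number of events affected cannot be estimated from the documents. The conclusion rests on the current text alone and assumes that no operational document already replaces the sentence. The correction is worth making because a safety classification is wrong as written and is cheap to put right.

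**What to change.** Replace the sentence in protocol Section 8.3.3.3 with one definition used there, for the first element of Section 8.4.1, and in SAP Section 6.7.1: an event is unexpected if its nature, severity or frequency is not consistent with the risks described in the study documents or with the anticipated course of the participant's condition. The other two elements of Section 8.4.1 stay as they are.

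Three consequential edits follow.

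- Remove relation to equipment function as a ground for 'expected', and leave that question to Section 8.3.3.2.
- If a measured-event clause is kept, align it with Section 8.1 so that it covers respiratory events only.
- Have the sponsor state whether respiratory hospitalization belongs on the list of expected events. That is a clinical safety judgement, and this review takes no position on it.

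The cost is one protocol paragraph, the matching wording in Section 8.4.1 and one line in the SAP, with the IRB approval that any protocol change needs. Severe AEs and SAEs already classified need one re-check against the new wording.

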8.3.4 TIME PERIOD AND FREQUENCY FOR EVENT ASSESSMENT AND FOLLOW-UP

All potentially related, severe AEs, and SAEs will be recorded on the appropriate CRF. Information to be collected includes event description, approximate date of onset, clinician's assessment of severity, relationship to study intervention (assessed by site investigator or qualified clinician designee), and date of the resolution/stabilization of the event. SAEs occurring while on the study must be documented appropriately regardless of relationship; and must be followed until one of the following criteria is met: study completion, resolution, the condition stabilizes, the event is otherwise explained or is judged by the site investigator or qualified clinician designee to be no longer clinically significant, or the participant is lost to follow up.

Any medical condition that is present at the time that the participant is screened will be considered as baseline and not reported as an AE. However, at the onset of the intervention and anytime during the study if the study participant's condition deteriorates and meets the definition of severe AE, SAE, or is possibly related to the study intervention, it will

Title: *The BREATHE Study: Bronchiolitis Recovery and the Use of High Efficiency Particulate Air (HEPA) Filters*

Sponsor: ISCPTN DCOC

be recorded as an AE. Changes in the severity of an AE will be documented to allow an assessment of the duration of the event at each level of severity to be performed. AEs characterized as intermittent require documentation of onset and duration of each individual episode.

The site investigator or qualified designee will record all potentially related, severe AEs, and SAEs with start dates occurring any time after informed consent is obtained until 30 days after the last day of study participation. At each study visit or interval phone call, the investigator will inquire about the occurrence of potentially related, severe AEs, and SAEs since the last visit. Events will be followed for outcome information until resolution or stabilization.

8.3.5 ADVERSE EVENT REPORTING

All potentially related or severe AEs that occur after informed consent is obtained until the last day of study participation will be documented in the participant's source documents and in the AE section of the CRF.

8.3.6 SERIOUS ADVERSE EVENT REPORTING

The site investigator or qualified delegate will immediately report to the appropriate entities (which may include the DCOC, NIH, DSMB, and local and/or reviewing IRBs) any SAE, when required to do so based on that entity's policies and procedures. Reports need to include the information required by the entities policies and procedures. Study endpoints that are serious adverse events (e.g., hospitalization) must be reported in accordance with the protocol unless there is evidence suggesting a causal relationship between the study intervention and the event (e.g., death from anaphylaxis). In that case, the investigator must immediately report the event.

All SAEs will be followed until satisfactory resolution or until the site investigator deems the event to be chronic or the participant is stable. Other supporting documentation of the event may be requested by the DCOC and should be provided as soon as possible.

8.3.7 REPORTING EVENTS TO PARTICIPANTS

The parent(s)/guardians of participants will be notified of those study-related (or potentially study-related) SAEs or unanticipated problems (UPs) that may affect either the parent/guardian's willingness to allow their child to continue with the study or the future health of the participant. This determination can be made by any of the following: the reviewing IRB, the medical monitor, the DSMB, the DCOC, or the NIH. The person or oversight body that makes the determination will inform the DCOC, which will instruct the site PIs/study coordinators to contact those participants enrolled through their site. Contacts with parent(s)/guardian(s) of participants, if necessary, will be recorded on the appropriate CRF and/or study log.

